### 7.2 Visit 2: Day 2 (+1) Clinic Visit

The following assessments will be performed.

- Obtain interim medical history and note any changes since the last visit.
- Record concomitant medications.
- Symptom-directed physical examination, if needed.
- Vital signs: temperature and pulse.
- Examine placebo microneedle patch application site. Subjects with localized rash, scarring or evidence of infection at placebo microneedle patch application site are to be evaluated by a study investigator. Per investigator discretion, photographic documentation (refer to MOP) and dermatologic referrals may be obtained.
- Study personnel will review the memory aid information with the LAR and record all AE/SAEs.
- The follow-up acceptability questionnaire will be completed by the LAR.

### 7.3 Visit 3: Day 8 (+2), Clinic Visit

The following assessments will be performed.

- Obtain interim medical history and note any changes since the last visit.
- Record concomitant medications.
- Symptom-directed physical examination, if needed.
- Vital signs: temperature and pulse.
- Examine placebo microneedle patch application site. Subjects with localized rash, scarring or evidence of secondary infection at microneedle patch application site are to be evaluated by a study investigator. Per investigator discretion, photographic documentation (refer to MOP) and dermatologic referrals may be initiated for subjects with localized reactions.
- Study personnel will review the memory aid information with the LAR and record all AE/SAEs. If symptoms persist, clinic staff will attempt to follow up with the subject daily until two days symptom-free. Maximum severity post Day 8 and stop date of the symptoms will be recorded by clinic staff on the Solicited Events eCRF.
- The follow-up acceptability questionnaire will be completed by the LAR. The LARs of subjects who have no ongoing solicited or unsolicited general AE or local AEs will have the opportunity to decide to have second and third placebo microneedle patches placed at different body sites from the initial location.
- Subjects with solicited or unsolicited general AE or local AEs or declining the optional microneedle patch 2/3 will then proceed to the Final Study Visit (Days 27 – 38).

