*\*All age ranges are inclusive. 4 children from each age group must complete Day 8 without halting criteria having been met (as detailed in Section 9.5) before subjects will be enrolled into the next younger age group.*

*\*\* Total number enrolled into each Cohort will be ≤25.*

Subjects will have an initial microneedle patch placed on Day 1. At Day 8, the LARs of subjects who have no ongoing solicited or unsolicited general AEs or local AEs will have the opportunity to decide to have second and third placebo microneedle patches placed at different body sites from the initial location.

Each subject will receive up to three placebo microneedle patches. Subjects will receive a first placebo microneedle patch on Day 1 and be assessed on Day 2 (+1 day), and Day 8 (+2 days). If the first patch is well tolerated without halting criteria having been met on Day 8 (+2 days), then the LAR will be provided the opportunity to have the subjects receive a second and third placebo microneedle patch on Day 8 and be assessed on Day 9 (+2 days) and Day 15 (+3 days). All subjects will have an end of study telephone call that will occur D27 – Day 38.

Safety will be measured by the occurrence of solicited application site and systemic reactogenicity on the day of microneedle patch administration through Day 8 for the first patch and through Day 15 (+3 days) for those that receive a second and third patch. If symptoms persist, clinic staff will attempt to follow up with the subject daily until two days symptom-free. Maximum severity post Day 8 (Day 15 in those that receive a second and third patch) and stop date of the symptoms will be recorded by clinic staff on the Solicited Events eCRF. Unsolicited AE, and serious adverse events (SAEs) and new-onset medical conditions (NOMC) will be collected through Day 27 and Day 38 after microneedle patch administration.

The acceptability of applying a microneedle patch topically will be assessed by LAR survey completed before each microneedle patch application, after microneedle patch removal, Day 2, and at Day 8 (+2 days) (and at Days 9 and 15 (+3 days) in those having an additional application).

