## **9.4 Individual Halting Rules**

Enrolled subjects will not be eligible to receive placebo microneedle patches 2/3 placement at Day 8 (+2 days) if any of the following occur:

- An ongoing  $\geq$ Grade 1 local site reaction (see Appendix B).
- An ongoing  $\geq$ Grade 1 solicited general AE (see Appendix C) or unsolicited AE.

Subjects unable to receive placebo microneedle patches 2/3 due to meeting an individual halting rule will continue to follow up according to the protocol through Day 27 – 38.

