## 14 SUPPLEMENTS/APPENDICES

### 14.1 Appendix A: Study Schedule

Visit #	1	2	3	4 &	5 &	Final*		
Procedures	D1	D2 +1	D8 +2	D9 +2	D15 +3	D27 - D38	Unscheduled Visit (If needed)	Premature Discontinuation
Signed Consent Form	X							
Inclusion/Exclusion Review	X							
Complete Medical History	X							
Concomitant Medications	X	X	X	X &	X &	X	X	X
Interim Medical History		X	X	X &	X &	X	X	X
Sign Optional Consent For Microneedle Patch 2/3	(X )		(X)					
Application of microneedle patch	X		X &					
Distribute memory aid, ruler & thermometer	X		X &					
Review memory aid		X	X	X &	X &	(X)	(X)	(X)
Physical Exam	Complete Physical Exam	X						
	Assessment of microneedle patch application site	X* *	X	X* *&	X &	X &	X	X
	Symptom-Directed Physical Exam		(X)	(X)	(X) &	(X) &	(X)	(X)
	Height and weight	X						
	Vital Signs ^	X	X	X	(X) &	(X) &	X	X
Photograph site of placebo microneedle patch	(X )	(X)	(X)	(X)	(X)	(X)	(X)	(X)
Assessment of Adverse Events and SAEs	X* *	X	X	(X) &	(X) &	X	X	X
Acceptability Questionnaire	X	X	X	(X) &	(X) &	X	X	X

\* The final study visit will be a telephone call at D27 – D38

\*\* Occurring 15 minutes and 30 minutes after microneedle patch removal.

& At Day 8 the LARs of subjects who no ongoing solicited or unsolicited general AE or local AEs will have the opportunity to decide to have second and third placebo microneedle patches placed at different body sites from the initial location. In those that elect to have a second/third placebo microneedle patch placed, they will return for clinic visits on Day 9 and Day 15.

^ Vital signs will include temperature and pulse.

(X) – As indicated/appropriate.

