## 14.2 Appendix B: Adverse Event & Reactogenicity Grading - LOCAL SITE REACTIONS

	LOCAL SITE REACTIONS			
	Grade			
	0	1	2	3
Induration/ Swelling *	None to less than 2.5 cm	2.5 – 5 cm and does not interfere with activity	5.1 – 10 cm or interferes with activity	> 10 cm or prevents daily activity, erosion, or ulceration
Erythema**	None to less than 2.5 cm	2.5 – 5 cm	5.1 – 10 cm	> 10 cm, erythroderma, or a diffuse rash >15% of the body surface area
Ecchymosis	None	2.5 – 5 cm	5.1 – 10 cm	> 10 cm
Tenderness	None	Mild discomfort to touch	Discomfort with movement	Significant discomfort at rest
Pain	None	Does not interfere with activity	Repeated use of non-narcotic pain reliever > 24 hours or interferes with activity	Any use of narcotic pain reliever or prevents daily activity
Pruritus (Itching)	None	Mild	Moderate itching; limiting instrumental activities of daily living	Severe itching; limiting self-care activities of daily living

\*Induration/swelling should be evaluated and graded using the functional scale as well as the actual measurement

\*\*In addition to grading the measured local reaction at the greatest single diameter, the measurement should be recorded as a continuous variable.

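### Eligibility for patches 2/3 is worded inconsistently, and Section 11.3 does not separate reactions after patch 1 from reactions after patches 2/3

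*Combined protocol and SAP*

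**What the plan says.** Eligibility for the optional second and third patches appears in several places.

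- **No ongoing AE, no grade threshold.** The Schematic of Study Design says that LARs of "subjects who have no ongoing solicited or unsolicited general AEs or local AEs will have the opportunity". Section 7.3 repeats this ("The LARs of subjects who have no ongoing solicited or unsolicited general AE or local AEs"), and so does the Appendix A footnote ("At Day 8 the LARs of subjects who no ongoing solicited or unsolicited general AE or local AEs").
- **AE, without the word ongoing.** The last bullet of Section 7.3 sends "Subjects with solicited or unsolicited general AE or local AEs or declining the optional microneedle patch 2/3" to the final visit.
- **Ongoing and at least Grade 1.** Section 9.4 makes a child ineligible for an ongoing reaction that is at least a "Grade 1 local site reaction (see Appendix B"), or for an ongoing event that is at least a "Grade 1 solicited general AE (see Appendix C) or unsolicited AE".
- **Well tolerated.** The Schematic also says "If the first patch is well tolerated without halting criteria having been met on Day 8 (+2 days"), the LAR will be offered further patches. The term is not defined. Elsewhere in the Schematic, and in Section 4, similar wording governs additional patches and points to the study-level rules in Section 9.5, not the individual rules in Section 9.4.

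Appendix B defines Grade 0 for induration and for erythema as "None to less than 2.5 cm". For ecchymosis, Grade 0 is none and Grade 1 starts at 2.5 cm.

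Section 11.3 plans numbers and percentages of subjects by treatment group in everyone who received a patch. It gives no denominator or separate presentation for patches 2/3.

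**The concern.** Two staff members who follow different sections could decide differently about re-exposing the same infant. The unclear cases are a child whose reaction has resolved and a child with a small reaction still visible on Day 8. Small, short-lived reactions are the kind the protocol expects: Section 2.3.1 describes localized, mild erythema that clears within hours or sometimes days.

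The statistical stake is narrower. Patches 2/3 go to body sites different from the child's first, so they feed the secondary endpoint on AEs by application site (Section 3.2.2). If eligibility depends on the response to patch 1, recipients are a selected group. A summary that does not separate the applications hides this.

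**Working it through.** The plan gives no figure for eligibility or for reaction rates, so there is nothing to reproduce. The check is to run the same children through each wording.

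| Child on Day 8 | No ongoing AE (Schematic, 7.3, Appendix A) | Last bullet of 7.3, read literally | Section 9.4 |
|---|---|---|---|
| No reaction at any time | offered | offered | not barred |
| Erythema of 2.5 to 5 cm, cleared by Day 3 | offered | final visit | not barred |
| Erythema of 2 cm, still present | depends on whether a Grade 0 reaction is a local AE | same question | not barred (Grade 0) |
| Bruise of 2 cm, still present | depends on whether an ungraded bruise is a local AE | same question | cannot be classified (no grade) |
| Erythema of 2.5 to 5 cm, still present | not offered | final visit | barred (Grade 1) |

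The wordings agree in the first and last rows. The second row separates the two bullets of Section 7.3. The third and fourth rows turn on a definition that the protocol does not give. Section 9.1.1 defines an AE broadly enough to include any abnormal sign. Section 9.2 grades all safety parameters by Appendices B and C, and the LAR scale in Section 8.1.5 labels Grade 0 as not present. These point in opposite directions for a 2 cm erythema.

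**Can the number of children be stated?** Let q be the share with any reaction ongoing at Day 8, and g the share of those that are below Grade 1. In a cohort of 25, the no-ongoing wording (counting small reactions as AEs) and Section 9.4 differ by 25 × q × g children. Both inputs are assumptions:

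- q = 5%, g = 25%: 25 × 0.05 × 0.25 = 0.3 children
- q = 10%, g = 50%: 25 × 0.10 × 0.50 = 1.25 children
- q = 40%, g = 90%: 25 × 0.40 × 0.90 = 9 children

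The range is too wide to be a finding, and nothing in the documents narrows it.

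**Selection on the patch 1 outcome.** As an illustration, assume that half the children react to any patch with probability 80% and half with probability 20%, that 20% of reactions persist to Day 8, and that refusal is unrelated to reaction.

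- Unselected rate: 0.5 × 0.8 + 0.5 × 0.2 = 50%.
- No-ongoing rule: share of high reactors among the eligible = 0.5 × (1 − 0.8 × 0.2) / (1 − 0.5 × 0.2) = 0.42 / 0.90 = 0.467. Rate after patches 2/3 = 0.467 × 0.8 + 0.533 × 0.2 = 48%.
- Literal last bullet: share of high reactors = 0.5 × 0.2 / 0.5 = 0.2. Rate = 0.2 × 0.8 + 0.8 × 0.2 = 32%.

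Selection is present under both rules; its strength differs. Reconciling the text would therefore not remove it.

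**The case against.** The strongest reply is that this is loose drafting. The last bullet of Section 7.3 directly follows a sentence that says ongoing, and the Schematic, Section 9.4 and Appendix A all say it too. The natural reading is a dropped word. Section 9.4 lists grounds for ineligibility without saying that every other child must be offered patches, so its conditions and the no-ongoing condition can be applied together. The references to Section 9.5 mainly concern when additional patches and sites open after the first two children. If Grade 0 means not present, Sections 7.3 and 9.4 agree on the 2 cm erythema.

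Much of this stands. It reduces the issue from rival rules to a missing word, an unsettled status for reactions below Grade 1 and an undefined tolerance condition. It does not settle the small reaction, because Section 9.1.1 supports the opposite reading, and the Grade 0 argument does not reach a small bruise, which has no grade.

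A reader might infer more, without support in the documents:

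- **That few children would qualify.** If 30% to 90% of children had some reaction, a literal any-AE rule would leave 25 × 0.70 = 17.5 down to 25 × 0.10 = 2.5 of 25. This rests on the probable drafting slip and on assumed rates. The statement in Section 2.3.1 that itching or mild erythema is typical comes from adults given patches of different composition.
- **That only non-reactors receive patches 2/3.** Under the no-ongoing wording, a child whose reaction resolved remains eligible.
- **That the inconsistency causes the selection.** Any AE-based rule selects on patch 1.
- **That patches 2/3 are the main source of data on other body sites.** In Cohort 1, Section 4 allows other sites in later participants once at least the first two children in a group have had the shoulder blade; Cohort 2 may use any listed site.

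**Conclusion.** The inconsistency is real and should be corrected. The protocol does not settle whether a resolved AE, or an ongoing reaction below Grade 1, blocks re-exposure of an infant, and it adds an undefined tolerance condition tied in places to Section 9.5 instead of Section 9.4. The number of children affected cannot be stated; every rate used above is an assumption.

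The statistical consequence is limited. The analysis is descriptive, no test or power depends on it, and data after patch 1 are unaffected. What is exposed is the description of reactions after patches 2/3 and the by-site secondary endpoint. Where a tendency to react carries over between patches, rates in selected recipients would tend to look lower than in unselected children. In the illustration this is slight under the no-ongoing wording (48% against 50%). That carry-over is itself an assumption.

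**What to change.** 1. Reconcile the Schematic of Study Design, Section 4, both bullets of Section 7.3, Section 9.4 and the Appendix A footnote into one eligibility statement, and refer to it from the other places. It should say whether a resolved AE counts, whether an ongoing reaction below Grade 1 counts (including a bruise too small to have a grade), what well tolerated means, and whether Section 9.4, Section 9.5 or both apply. Which rule applies is for the sponsor and investigator.
2. In Section 11.3, report reactions after patch 1 and after patches 2/3 separately. Give the numbers eligible, ineligible by reason, and declining. Where numbers allow, split the patch 2/3 results by whether the child reacted to patch 1.

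The first item costs only wording. The second mostly reuses safety data already planned; the reason for ineligibility or refusal must be recorded on Day 8. Its drawback is small cells, so the table should be read as description only. If the reconciled rule excluded every child with any patch 1 reaction, the reactor stratum would be empty and the split should be dropped.

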#### Optional Microneedle Patch 2/3 Study Events Day 8 (+2 days)

- The optional consent for the optional placebo microneedle patches 2/3 will be signed before additional study procedures occur on Day 8 (if not already signed).
- Inclusion/Exclusion criteria review.
- A baseline photograph of the area of application may be obtained.

- Application of placebo microneedle patches 2/3 to the skin in a different location than previously by a trained study nurse. The placebo microneedle patches will remain in place for up to 20 minutes. The patches will then be removed and the used patch will be saved.
- The memory aid, thermometer and ruler will be provided to the LAR and instructions will be provided.
- The site of the placebo microneedle patches removal will be assessed at least 15 minutes and 30 minutes post-placebo microneedle patch removal. Per investigator discretion, photographic documentation (refer to MOP) and dermatologic referrals may be obtained.
- Study personnel will assess and record all AE/SAEs that occur after enrollment.
- The acceptability questionnaire will be completed by the LAR.

#### **7.4 Visit 4: Day 9 (+2) Clinic Visit (Only in those with Placebo Microneedle Patches 2/3 placement)**

The following assessments will be performed.

- Obtain interim medical history and note any changes since the last visit.
- Record concomitant medications.
- Symptom-directed physical examination, if needed.
- Vital signs: temperature and pulse.
- Examine placebo microneedle patch application sites. Subjects with localized rash, scarring or evidence of infection at placebo microneedle patch application site are to be evaluated by a study investigator. Per investigator discretion, photographic documentation (refer to MOP) and dermatologic referrals may be obtained.
- Study personnel will review the memory aid information with the LAR and record all AE/SAEs.
- The acceptability questionnaire will be completed by the LAR.

#### **7.5 Visit 5: Day 15 (+3), Clinic Visit (Only in those with Placebo Microneedle Patches 2/3 placement)**

The following assessments will be performed.

- Obtain interim medical history and note any changes since the last visit.
- Record concomitant medications.
- Symptom-directed physical examination, if needed.
- Vital signs: temperature and pulse.
- Examine placebo microneedle patch application site. Subjects with localized rash, scarring or evidence of secondary infection at placebo microneedle patch application site are to be evaluated by a study investigator. Per investigator discretion, photographic documentation (refer to MOP) and dermatologic referrals may be obtained.

- Study personnel will review the memory aid information with the LAR and record all AE/SAEs. If symptoms persist, clinic staff will attempt to follow up with the LAR daily until the child is symptom-free for 2 days. Maximum severity post Day 15 in those that receive a second and third patch and stop date of the symptoms will be recorded by clinic staff on the Solicited Events eCRF.
- The follow-up acceptability questionnaire will be completed by the LAR.

## 7.6 Final Visit: Day 27 - 38, Telephone Call

The following assessments will be performed.

- Obtain interim medical history and note any changes since the last visit.
- Record concomitant medications.
- Study personnel will review the memory aid information with the LAR (if ongoing symptoms were noted at Day 8 for placebo microneedle patch 1 and Day 15 for placebo microneedle patch 2/3) and record all AE/SAEs.
- The final acceptability questionnaire will be completed by the LAR.

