#### 3.2.2 Secondary Endpoints

- Occurrence of Grade 3 placebo microneedle patch-related unsolicited adverse events from Day 1 through the Final Study Visit (Day 27 – 38).

- Occurrence of new-onset medical conditions (NOMC) from Day 1 through the Final Study Visit (Day 27 – 38).
- Occurrence of solicited and unsolicited adverse events described at the site at which the placebo microneedle patch was applied.
- Quantitative and qualitative description of LAR responses to survey questions.

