## 4 STUDY DESIGN

This is a single-center, unblinded, study in which healthy infants and children (6 weeks – 24 months inclusive) will have placebo microneedle patches applied to the skin. This study is designed to investigate the safety, reactogenicity, and acceptability of a placebo microneedle patch.

Infants and children will be recruited from metropolitan Atlanta and will be enrolled at Emory Children's Center. Approximately 25 to 50 infants and young children will be enrolled into one of two possible cohorts that will have placebo microneedle patches administered topically for up to approximately 20 minutes. Cohort 1 will assess one formulation of the microneedle patch (Microneedle Formulation 1). If the Microneedle Formulation 1 is well tolerated in Cohort 1, Cohort 2 may be enrolled using a different formulation of the microneedle patches if available (Microneedle Formulation 2).

After informed consent is obtained, subjects will be screened by history and physical examination at screening. Collected data will include demographic information, medical history, list of current and recent medications, and vaccination history. The placebo microneedle patch will be administered on Day 1 to subjects meeting enrollment criteria. Each subject will have 3 clinic visits: Day 1, Day 2 (+1 day), and Day 8 (+2 days). One telephone call will occur (Day 29 +/- 3 days). In those that receive additional microneedle patches on Day 8 (+2 days), follow-up visits will also occur at Day 9 (+2 days) and Day 15 (+3 days). Refer to the Appendix A for a detailed listing of study days and procedures.

Safety will be measured by the occurrence of solicited application site and systemic reactogenicity on the day of microneedle patch administration through Day 8 (+2 days) for the first patch and through Day 15 (+3 days) for the second and third patch. Unsolicited AE, and serious adverse events (SAEs) and new-onset medical conditions (NOMC) will be collected through Day 29 and Day 38 after microneedle patch administration. The acceptability of applying a microneedle patch topically will be assessed by LAR survey completed before microneedle patch application on Day 1, after microneedle patch removal on Day 1, at Day 2 (+1 day), Day 8 (+2 days), and the Final Study Visit (Day 27 – 38) in everyone. In those that receive additional microneedle patches, it will be also be repeated at Day 9 (+2 days) and Day 15 (+3 days).

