### 5.3 Subject Exclusion Criteria

A subject will not be eligible to participate in this study if any the following criteria apply:

1. Subject has an acute illness with fever (temperature >100.4 °F) within 72 hours prior to enrollment.
2. Subject has a known chronic medical problem.
3. Subject has known immunosuppression due to underlying illness or treatment, including (but not limited to): Human Immunodeficiency Virus (or birth to a HIV-positive mother), hepatitis B or C; organ transplant; active cancer or any history

of hematologic cancer; receipt of chemotherapy or radiation therapy; congenital immunodeficiency, anatomical or functional asplenia.

4. Subject has used long-term\* high-dose\*\* oral or parenteral glucocorticoids, or high-dose inhaled steroids.\*\*\*

*\* Long term is defined as taken for 2 weeks or more in total at any time during the past 2 months.*

*\*\* High dose defined as prednisone  $\geq$  20 mg total daily dose, or equivalent dose of other glucocorticoids.*

*\*\*\* High dose defined as  $>800$  mcg/day of beclomethasone dipropionate or equivalent.*

5. Subject has a history of an underlying skin condition (e.g., eczema, atopic dermatitis) or an open lesion (e.g., laceration, abrasion), scar, or rash in the areas of the planned microneedle patch administration which will interfere with the assessment of reactogenicity.
6. Subject or family members have a history of keloid formation.
7. Subject has any condition that, in the opinion of the investigator, may put the subject at increased risk of harm, may cause the subject to be unable to meet the requirements or might otherwise interfere with evaluations required by the study.
8. Subject has received any experimental products within 30 days before study entry or plan to receive experimental products at any time during the study.
9. Subject has received a vaccine within 7 days of enrollment or plans to receive a vaccine within 7 days after enrollment.
10. Subject has previously received immunoglobulin or blood products.

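### After the last scheduled skin examination (7–9 days after a single patch, 5–10 days after patches 2/3), late, missed or non-solicited marks rest on a general adverse event enquiry by telephone

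*Combined protocol and SAP*

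**What the plan says.** **Scarring is something staff look for.** One exclusion in section 5.3 reads "Subject or family members have a history of keloid formation". Section 7.3 (Day 8) states: "Subjects with localized rash, scarring or evidence of secondary infection at microneedle patch application site are to be evaluated by a study investigator". Sections 7.2, 7.4, 7.5, 7.7 and 7.8 carry an equivalent instruction, and each names scarring. Neither scar nor colour change is among the six solicited local symptoms in section 8.1.5.

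**Visits.** The design schematic says "Subjects will have an initial microneedle patch placed on Day 1". Section 4 says "Each subject will have 3 clinic visits: Day 1, Day 2 (+1 day), and Day 8 (+2 days"). Under section 7.3, children with an adverse event at Day 8 take the same route as those "declining the optional microneedle patch 2/3 will then proceed to the Final Study Visit (Days 27 – 38"). Children who receive patches 2/3 on Day 8 (+2) return on Day 9 (+2) and Day 15 (+3).

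**Final contact.** Appendix A notes: "The final study visit will be a telephone call at D27" to D38. Section 7.6 lists interim history, concomitant medications, memory aid review with recording of adverse events, and the acceptability questionnaire. The memory aid part is conditional: staff "review the memory aid information with the LAR (if ongoing symptoms were noted at Day 8", or at Day 15 for patches 2/3. Appendix A also shows a site photograph, as indicated, in the D27–D38 column.

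**What depends on it.** A secondary endpoint in section 3.2.2 is "Occurrence of solicited and unsolicited adverse events described at the site at which the placebo microneedle patch was applied", and section 3.1.2 has an objective on the suitability of different body locations. Section 9.2.1 collects unsolicited events through the Day 27–38 contact.

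**The concern.** Section 7.6 is the only post-baseline contact in section 7 with no application-site item. A child who leaves early is offered a site examination that names scarring (section 7.7, if the LAR agrees). A child who completes the study has no listed question about the patch sites at the last contact.

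A faint, painless mark is not obviously an illness or a change in health, so a parent asked in general terms may not mention it. If nothing is reported, the data cannot separate a site with no mark from a site nobody asked about. That weakens the late part of the site-specific endpoint and the comparison of body locations.

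**Working it through.** The plan gives no figure on this point. The probabilities in section 11.2 answer a different question and are not used here. The check is day arithmetic on the visit windows, followed by a comparison of what each provision covers.

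**Step 1. Inputs.** Patch 1: Day 1 (schematic). Day 8 visit: Days 8–10 (sections 4, 7.3). Patches 2/3: applied at that visit, so Days 8–10. Day 15 visit: Days 15–18 (section 7.5). Call: Days 27–38 (section 7.6, Appendix A).

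**Step 2. Windows.** Time since application = visit day − application day. Gap to the call = call day − visit day.

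| Children and site | Last scheduled look | Days since application | Days from last look to call |
|---|---|---|---|
| One patch | Day 8–10 | 8 − 1 = 7 to 10 − 1 = 9 | 27 − 10 = 17 to 38 − 8 = 30 |
| Patches 2/3, new sites | Day 15–18 | 15 − 10 = 5 to 18 − 8 = 10 | 27 − 18 = 9 to 38 − 15 = 23 |
| Patches 2/3, first site | Day 15–18 | 15 − 1 = 14 to 18 − 1 = 17 | 9 to 23 |

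The third row assumes that the Day 15 examination includes the first site; section 7.5 does not limit it to the new ones. The 5-day minimum assumes that the Day 15 window is counted from Day 1, as written.

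Section 4 also gives the call as Day 29 ± 3, that is, Days 26–32. The gaps would then be 26 − 10 = 16 to 32 − 8 = 24 days and 26 − 18 = 8 to 32 − 15 = 17 days. The conclusion does not change.

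**Step 3. Which marks are covered.**

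| Mark | Provision after the last scheduled look |
|---|---|
| Solicited local symptom still present at Day 8 or 15 | Staff attempt daily contact until two days without symptoms, record maximum severity and stop date, and review the memory aid at the call (7.3, 7.5, 7.6) |
| Scar or rash seen at a visit | Investigator evaluation (7.2–7.5); once recorded as an adverse event, followed to resolution or stability (9.3.3) |
| Mark first appearing after the last visit, or missed there | General interim history and adverse event enquiry only |
| Scar or colour change, even when the memory aid is reviewed | Not a solicited symptom (8.1.5), so general enquiry only unless already recorded |

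**Step 4. Who has the earliest last look.** Sections 7.3 and 9.4 send children with an ongoing local reaction at Day 8 to the final call without patches 2/3. They have no scheduled Day 9 or Day 15 examination. Their persisting symptoms are followed by contact, but no further site examination is scheduled.

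**The case against.** The case on the other side is substantial, and much of it stands.

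- **The call does ask.** Section 7.6 takes interim history and adverse events from every LAR, and section 9.2.1 says the details come by interview. The condition on ongoing symptoms restricts only the memory aid review. A reader might infer that lasting marks are left to unprompted report; the documents do not support that. The prompt exists but is not site-specific.
- **Persisting reactions are followed.** A reader might also infer that all lasting marks are lost. Step 3 shows otherwise for solicited symptoms present at the last visit and for scarring seen there. In children with patches 2/3 the first site can be seen again at 14–17 days, and unscheduled visits include a site examination (section 7.8).
- **Some material is not in the documents.** The questionnaire, memory aid, call script, eCRF and manual of procedures are not available, so a site question there cannot be ruled out. Section 8.1.6 describes the questionnaire as covering acceptability. The finding is that section 7.6 lists no site item, not that nobody will ask.
- **Appendix A is only partly legible.** Its site-assessment row shows seven marks for eight columns. A blank at the final call fits sections 7.6–7.8, but the extracted table does not prove it.
- **Scarring is not an endpoint.** It appears only as a trigger for evaluation, section 2.3.1 expects transient irritation, and section 11.2 claims no more than rough safety estimates. This limits the weight of the point. It does not remove it, because unsolicited site events through Day 27–38 feed a stated secondary endpoint.

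**Conclusion.** The point holds in a limited form. For marks that appear after the last visit, were missed there, or are not solicited, ascertainment rests on a general telephone enquiry made 17–30 days after the last scheduled look (one patch) or 9–23 days after it (patches 2/3). Absence of a report at Day 27–38 is therefore weak evidence on late site effects. The primary endpoints based on solicited events are not touched, since they end 8 days after application.

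It is tempting to put a probability on a missed scar. The documents give neither a rate of late marks nor the share of LARs who would mention one, so no such figure is justified. The conclusion rests on the visit windows as written and on section 7.6 being the complete list for the call.

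Separately, Appendix A's as-indicated photograph at D27–D38 does not fit a telephone contact, and section 7.6 gives no way to obtain one. The two need to be reconciled. This is a worthwhile, inexpensive improvement rather than a defect that undermines the study.

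**What to change.** 1. In section 7.6 and Appendix A, add a scripted yes/no question for each application site at the final call: any remaining mark, colour change, raised area or scar.
2. Add one eCRF field per site, and record a yes as a site adverse event, linked to the existing record if the finding is already being followed.
3. In section 11.3, tabulate site status at final contact by application site, with the number of sites asked about as denominator.
4. Reconcile the photograph entry with the telephone format, for example as a photograph supplied by the LAR when indicated.

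**Cost:** one script item and one field per site, with no added scheduled visit. LAR report is less exact than an examination, and the question may prompt a few photographs or unscheduled visits, which section 7.8 already provides for. If the call script or eCRF already contains such a question, only the text of section 7.6 and Appendix A and the tabulation need to change.
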